***Data analysis**

Cumulative incidence rates and corresponding 95% confidence intervals as well as Kaplan-Meier rates and corresponding 95% confidence intervals will be calculated for the occurrence of hepatic decompensation, thromboembolic events, or mortality, as separate events, at multiple time points during and at the end of the 3-year follow-up period. Baseline factors potentially predictive of events will be identified through Kaplan-Meier survival estimates for patients with vs. without the factor and testing for statistical significance using the log-rank test. Cox proportional hazards models will be constructed to evaluate the influence of these identified factors simultaneously.

Patient demographics and characteristics will be described at the time of initiation of eltrombopag. Virology, laboratory information, information on dose and duration of eltrombopag, early and sustained virologic response, anti-viral therapy and incidence of hepatic decompensation and thromboembolic events will be described at baseline and distinct follow-up time points. Continuous variables will be reported as mean, standard deviation, median, 25th and 75th quartiles, and range. Categorical variables will be summarized as number and proportion of subjects with observed (non-missing) data, with corresponding 95% confidence intervals (CI) by exact methods.

The number and percentage of patients who achieve early virologic response and sustained virologic response will be reported at distinct follow-up time points. The probability of attaining EVR and SVR by these time points will be presented as Kaplan-Meier estimates, along with median time to attaining virologic response.

***Milestones.** An interim analysis will be conducted in 2016 and the final analysis will be completed in 2018.

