8.3.1. Outcomes

The main outcomes of this study are:

- Hepatic decompensation, defined as new onset or worsening of baseline of any of the following:
 - Ascites
 - Hepatic encephalopathy
 - Variceal Bleeding
- Thromboembolic events
 - Myocardial infarction (MI)
 - Ischemic Stroke (IS)
 - Portal vein thrombosis (PVT)
 - Deep vein thrombosis (DVT)
 - Pulmonary embolism (PE)
- Mortality (all cause and cause-specific)
- Treatment effectiveness among eltrombopag users, assessed as
 - Percentage of eltrombopag users able to initiate antiviral therapy
 - Percentage of eltrombopag users requiring no, one, two, three, or four or more interferon dose reductions
 - Percentage of eltrombopag users reaching early virologic response, defined as clinically significant reduction in HCV RNA (≥ 2 log₁₀ drop or undetectable) after 12 weeks of antiviral treatment
 - Percentage of eltrombopag users achieve SVR, defined by HCV RNA negative 24 weeks after cessation of treatment
 - Change in platelet counts before and during antiviral therapy among those able to initiate antiviral therapy

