The number and percentage of patients who achieve early virologic response and sustained virologic response will be reported at distinct follow-up time points. The probability of attaining SVR by these time points will be presented as Kaplan-Meier estimates, along with median time to attaining SVR.

For the long term outcomes of hepatic decompensation or mortality at 3 years (as separate events), incidence rate ratios comparing eltrombopag patients who did vs. did not attain SVR will be calculated, along with 95% confidence intervals using the method outlined by Dobson et al [Dobson, 1991]. For eltrombopag patients with less than three years of follow-up, survival analyses will be used to take censoring into account. Kaplan-Meier survival graphs will be plotted and the log rank test will be used to determine statistical significance of SVR (after assuming proportionality assumptions). Factors determined to be related to hepatic decompensation (or to all-cause mortality in a separate analysis) from the earlier exploratory work will be included in a multivariate Cox proportional hazards model along with SVR to determine independence of SVR as a predictor variable.

For those patients who are lost to follow-up, or who drop out of the study, the analyses will include all data up to the point of their last data collection.

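### SVR (and, in the abstract, EVR) is a fixed-time yes/no outcome, yet Kaplan-Meier probabilities and median times are planned for it; SVR is overstated to the extent that patients who die, or leave after failing, are censored

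*Protocol*

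**What the plan says.** Protocol section 8.3.1 defines SVR as a percentage of eltrombopag users: "Percentage of eltrombopag users achieve SVR, defined by HCV RNA negative 24 weeks after cessation of treatment". EVR is likewise a percentage, assessed "after 12 weeks of antiviral treatment". Both are a status at one assessment.

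Section 8.7 first plans the natural summary: "The number and percentage of patients who achieve early virologic response and sustained virologic response will be reported at distinct follow-up time points". For categorical variables the same section gives exact 95% intervals and uses patients with non-missing data as the denominator. It then adds a time-to-event presentation of SVR alone: "The probability of attaining SVR by these time points will be presented as Kaplan-Meier estimates, along with median time to attaining SVR".

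The Data analysis paragraph of the abstract applies the same presentation to both outcomes: "The probability of attaining EVR and SVR by these time points will be presented as Kaplan-Meier estimates, along with median time to attaining virologic response". The two places therefore disagree on EVR.

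For patients who drop out or are lost, section 8.7 says that "the analyses will include all data up to the point of their last data collection". In a Kaplan-Meier analysis this is censoring at the last contact. For SVR and EVR, the protocol names neither death nor virologic failure as a competing or terminal event.

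**The concern.** Kaplan-Meier gives a valid probability only if censored patients have the same later chance of the event as those still observed. A patient who has died cannot attain SVR, and one who leaves after virologic failure is very unlikely to attain it on that course. Censoring such patients shares out their weight among those still at risk, some of whom respond, and the estimate rises. The more patients fail and leave, the better the figure looks.

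Leaving is foreseeable. Section 8.2 limits the 3-year follow-up to patients who keep returning to their centre under local care.

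The median has a separate weakness. SVR can be declared only 24 weeks after treatment stops, so its timing is set by course length and visit scheduling. EVR is tied to week 12 in the same way.

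SVR is a secondary effectiveness outcome (sections 7 and 8.1), and the reports go to the EMA, the FDA and other agencies (section 11.2). The primary outcome, hepatic decompensation, is not affected.

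**Working it through.** **Inputs from the protocol.**
- Cohort size 105 (section 8.5), reproduced as 0.021 × 5000 = 105.
- SVR of 23% and 19% in the eltrombopag arms of the two phase III trials (section 6.1). The protocol describes patients on direct acting agents as not studied there, so these rates are only a low reference point.
- Deaths of 3% on eltrombopag in those trials (section 6.2).

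The protocol gives no numerical SVR or EVR estimate to reproduce.

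**Assumptions.** Courses of 24 weeks (40% of patients) or 48 weeks (60%); a 4-week lead-in; an SVR visit 24 to 32 weeks after stopping; true SVR of 19%, 23%, 40% or 60%; and 0 to 20% of patients dying or leaving before the assessment, none of them responders. Each scenario was simulated 400 times with N = 105.

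**Step 1: failures stay in the risk set to 3 years.** Let p be the true SVR and q the share dying or leaving early. If all early losses come before the first SVR, then 1 − KM = p/(1 − q). This is a ceiling, because some losses come later.
- p = 0.23, q = 0: 0.23, no excess.
- p = 0.23, q = 0.03: 0.23/0.97 = 0.237.
- p = 0.23, q = 0.20: 0.23/0.80 = 0.288.
- p = 0.60, q = 0.20: 0.60/0.80 = 0.75.

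Simulated means, shown as crude proportion → 1 − KM:

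| True SVR | q = 0 | q = 3% | q = 10% | q = 20% |
|---|---|---|---|---|
| 19% | 18.9 → 18.9 | 18.9 → 19.4 | 18.9 → 20.9 | 19.1 → 23.6 |
| 23% | 22.8 → 22.8 | 22.9 → 23.5 | 23.1 → 25.4 | 22.9 → 28.1 |
| 60% | 59.9 → 59.9 | 59.8 → 61.6 | 59.8 → 66.2 | 60.2 → 74.7 |

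**Step 2: failures are censored.** At a true SVR of 19-23%, 1 − KM is about 50-64% if failures are censored at their SVR visit. It is about 100% if they are censored when treatment stops, because almost only future responders then remain at risk.

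A case that can be checked by hand: 105 patients, 21 with SVR at week 48 and 21 at week 72. Of the 63 failures, 21 are censored before week 48, 21 between the two weeks and 21 after. At risk are 84 and then 42, so 1 − KM = 1 − (63/84)(21/42) = 62.5%. The true proportion is 42/105 = 40%. This shows the mechanism; it is not a forecast.

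**Step 3: the median.** At a true SVR of 19-23% with failures retained, the median was reached in no run. With failures censored at the SVR visit it was apparently reached in 46-87% of runs, and with censoring at treatment stop in all of them, although fewer than half of the patients responded. At a true SVR of 60% with failures retained, it exists and averages about 80-82 weeks. Under the assumptions, an SVR after a 48-week course falls between 4 + 48 + 24 = 76 and 84 weeks. The median thus restates the longer course plus its visit window.

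**Step 4: does the planned percentage escape the problem?** Not by itself, because its denominator is non-missing data. Take a true SVR of 20%, so 21 responders and 84 failures, and assume that 60% of failures (50) leave without a result. The observed-data proportion is 21/(105 − 50) = 21/55 = 38%. This is an upper bound, since it assumes that every leaver lacks a result.

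**The case against.** The strongest reply has four parts.

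- **Kaplan-Meier is not the only estimate.** The number and percentage are planned in the preceding sentence, and section 8.3.1 defines the outcomes as percentages. This stands. A reader might infer that the study's only SVR figure is the Kaplan-Meier one; the protocol does not support that.
- **No rule says that failures are censored.** The last-data rule covers patients who drop out or are lost. A patient who fails but stays in follow-up can remain in the risk set, and then adds no bias. This stands too. A reader might infer that everyone who fails or stops treatment is censored, and so that SVR must be grossly overstated. The text does not say so, and the large figures in steps 2 and 4 depend on assumptions that it does not contain.
- **The scenarios lose only non-responders.** If loss were unrelated to response, counting every leaver as a failure would understate SVR, and Kaplan-Meier would partly correct this. That is a fair limit on the size for patients who are simply lost. It does not help for deaths or for patients who leave because treatment failed.
- **The study is descriptive, and no comparison of time to SVR is planned.** That limits the consequences, but the SVR figure will still be read as a cure rate.

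Kaplan-Meier could also serve the 2016 interim analysis, when some patients are not yet assessable. Cumulative incidence with competing events meets that need without treating deaths and failures as potential responders.

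**Conclusion.** The point holds in conditional form. Kaplan-Meier with a median time does not suit an outcome "defined by HCV RNA negative 24 weeks after cessation of treatment", and the stated handling of leavers biases the SVR probability upward whenever patients die, or leave after failing, before the assessment.

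The size depends on how many do so and on when failures leave the risk set, which the protocol does not state. Step 1 gives the modest end, from nil to about 5 points at a true SVR of 19-23% and up to about 14.5 points at 60%. Step 2 gives the gross end. All these sizes rest on assumed course lengths, visit timing and loss. No calculation was made for EVR, for which the argument is one of principle.

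A reader might also conclude that the median has no meaning at all. That goes too far: above 50% SVR it exists, but says little beyond course length. The disagreement between the abstract and section 8.7 on EVR is real but editorial.

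**What to change.** 1. Delete the Kaplan-Meier estimates and median times for SVR in section 8.7 and for EVR and SVR in the abstract. This also removes the disagreement on EVR.
2. Make the headline the proportion of all eltrombopag users due for the assessment who have SVR 24 weeks after treatment, and likewise EVR at week 12, with exact 95% intervals. Count virologic failures, deaths and missing results as non-response. Define due by elapsed time, not by whether the patient came back.
3. Show the observed-data proportion as a sensitivity analysis.
4. If a time course is wanted, or an interim estimate that includes patients not yet assessable, use cumulative incidence with death and virologic failure as competing events.

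**Cost.** Rewording in two places, a sentence fixing the denominator and one extra tabulation; no new data. The small downside is that counting missing results as non-response is conservative if some leavers did respond, and the observed-data proportion shows by how much this could matter.

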8. RESEARCH METHODS

8.1. Study Design

The HCV-TARGET study is a carefully maintained longitudinal observational research registry to prospectively enrol and follow HCV patients treated with anti-HCV regimens in a real-world setting in order to rapidly inform strategies for better management of populations underrepresented in clinical trials, identify and remediate gaps in treatment

guidelines and adverse event management in order to optimize rates of SVR. It's comprised of patients that receive HCV therapy with direct acting antiviral agents. All adult patients (age 18 or older) who are prescribed HCV treatment with direct acting antiviral agents outside of a clinical trial are eligible for participation, provided they provide written informed consent and are not participating in any other registry or study where HCV treatment outcomes are reported, except where approved or conducted as an adjunct project of the HCV-TARGET registry.

This study is an eltrombopag cohort study nested within HCV-TARGET, comprising all patients treated with eltrombopag. Nesting the eltrombopag cohort study within the HCV-TARGET is an efficient way to identify and study eltrombopag users in a real-world setting. All patients treated with eltrombopag will be included in the nested cohort study. No patients who have not been exposed to eltrombopag will be included in the nested cohort study. Within the nested cohort study, patients will be followed for up to three years after eltrombopag initiation. The major safety outcome is hepatic decompensation. Incidence of thromboembolic events and mortality will also be determined. Thromboembolic events include myocardial infarction, ischemic stroke, pulmonary embolism, deep vein thrombosis, portal vein thrombosis, and other events. The major effectiveness outcomes include ability to initiate anti-viral therapy, ability to maintain anti-viral therapy, early virologic response and sustained virologic response. The incidence of hepatic decompensation and of mortality at three years will be compared between eltrombopag users who achieve SVR and those users who do not achieve SVR. An interim analysis will be conducted in 2016 and the final analysis will be completed in 2018.

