9. PROTECTION OF HUMAN SUBJECTS

9.1. Ethical approval and subject consent

The HCV-TARGET protocol and informed consent documents received approval by the local site IRB prior to initiation of the study at each site. Consent for participation in HCV-TARGET includes permission 1) to submit de-identified historical medical records related to patient demographics, medical/co-morbid condition history, prior HCV therapy and evaluation of liver disease, 2) to submit prospective de-identified medical records related to HCV treatment response, safety, side effects, side effect management and safety/efficacy outcomes of antiviral therapy; 3) for collection of biospecimens including genomic DNA to be archived for future studies (optional); and 4) to be followed for HCV co-morbid conditions and mortality for up to 3 years after treatment outcome is determined.

Written informed consent must be obtained before any data collection and may be given by patients after being prescribed HCV treatment up to 4 weeks after treatment initiation. The method of obtaining and documenting the informed consent and the contents of the consent complies with ICH GCP guidelines and all applicable laws and regulations.

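### The comparison of 3-year outcomes by SVR uses a status known only 24 weeks after treatment ends, with follow-up from eltrombopag initiation and no landmark or time-dependent SVR, so it is biased towards a protective SVR effect

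*Protocol*

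**What the plan says.** Protocol section 8.1 sets the cohort's clock: "Within the nested cohort study, patients will be followed for up to three years after eltrombopag initiation". The abstract (section 3) gives the same origin. Section 8.1 adds that the incidence of decompensation and of mortality "at three years will be compared between eltrombopag users who achieve SVR and those users who do not achieve SVR".

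Section 8.3.1 fixes when the grouping variable becomes known. SVR is "defined by HCV RNA negative 24 weeks after cessation of treatment".

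Section 8.7 sets out the comparison. For each outcome, "incidence rate ratios comparing eltrombopag patients who did vs. did not attain SVR will be calculated, along with 95% confidence intervals". Kaplan-Meier curves and a log-rank test for SVR follow, with proportionality taken as given. Factors found in the exploratory work then "will be included in a multivariate Cox proportional hazards model along with SVR to determine independence of SVR as a predictor variable".

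The time-related provisions are about incomplete follow-up: "For eltrombopag patients with less than three years of follow-up, survival analyses will be used to take censoring into account", and patients who are lost or drop out contribute data up to their last collection. Nothing says how to handle events or person-time before SVR can be known.

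Section 9.1 uses a different clock. Patients consent "to be followed for HCV co-morbid conditions and mortality for up to 3 years after treatment outcome is determined".

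**The concern.** Patients are grouped by something that happens during the follow-up over which their events are counted. Two mechanisms follow.

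- **Death.** A patient who dies before the assessment cannot be classed as SVR. Every SVR patient therefore carries a stretch of person-time, from eltrombopag initiation to the assessment, in which death was impossible by definition. All early deaths fall in the other group.
- **Decompensation.** An early event does not rule out SVR. If it interrupts or weakens antiviral therapy, however, it lowers the chance of SVR, and the event then helps to produce the non-SVR label.

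Both lower the rate in the SVR group and raise it in the comparison group. Baseline covariates in the Cox model do not help, because the fault lies in defining the groups by later information. For death, proportional hazards also fails by construction, since the SVR group has no hazard before assessment.

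At stake is a listed secondary aim (section 7). Its result would be tested for significance, described as showing whether SVR is an independent predictor, and sent to regulators (section 11.2).

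**Working it through.** The protocol gives no effect size or power for this comparison, so there is no stated figure to reproduce. The check asks what rate ratio the planned analysis would give if SVR had no effect (true ratio 1.0).

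**Inputs**

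- Window: 3 years from eltrombopag initiation (section 8.1).
- SVR time point: L = T + 24/52 years, where T is treatment duration (24 weeks from section 8.3.1). Section 8.4 says the registry does not define duration. Assumed: T = 24 or 48 weeks (0.462 or 0.923 years), antivirals starting with eltrombopag. Then L = 0.923 or 1.385 years, which is 31% or 46% of the window.
- Decompensation: 10% (sections 6.2 and 8.5). Assumed: reached by L, at constant hazard λ = −ln(0.9)/L = 0.1141 or 0.0761 per year.
- SVR probability s: section 6.1 gives 23% and 19% in the two earlier trials. Assumed range: 20, 40 and 60%.
- q: chance of SVR after an on-treatment event, relative to other patients. Assumed: 0, 0.5 or 1.

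**Formulas**, per patient, clock from eltrombopag initiation:

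- On-treatment events: E1 = 1 − exp(−λT), with person-time P1 = E1/λ − T·exp(−λT).
- All other patients: E2 = exp(−λT) − exp(−3λ), with person-time P2 = E2/λ + T·exp(−λT).
- SVR rate = (s·E2 + q·s·E1) / (s·P2 + q·s·P1).
- Non-SVR rate = ((1−s)·E2 + (1−q·s)·E1) / ((1−s)·P2 + (1−q·s)·P1).

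**Worked case** (48 weeks, s = 40%, q = 0): E1 = 0.0678, P1 = 0.0309, E2 = 0.1363, P2 = 2.6513. SVR rate = 0.0545/1.0605 = 0.0514. Non-SVR rate = 0.1496/1.6217 = 0.0922. Ratio 0.557, although both groups have the same true hazard of 0.0761.

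**Decompensation rate ratio with no true SVR effect**

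| Effect of an on-treatment event on SVR | Treatment | s = 20% | s = 40% | s = 60% |
|---|---|---|---|---|
| Precludes it (q = 0) | 24 weeks | 0.793 | 0.742 | 0.658 |
| | 48 weeks | 0.625 | 0.557 | 0.459 |
| Halves it (q = 0.5) | 24 weeks | 0.894 | 0.864 | 0.809 |
| | 48 weeks | 0.806 | 0.758 | 0.677 |
| None (q = 1) | either | 1.0 | 1.0 | 1.0 |

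**Death.** Any death before L precludes SVR, so L replaces T in the formulas and q = 0. Taking the 3% of section 6.2 as a 3-year risk (assumed), λ = −ln(0.97)/3 = 0.01015. At SVR of 19 to 23% the ratio is 0.64 to 0.63 for 24 weeks and 0.48 to 0.47 for 48 weeks.

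**Does a landmark cure it?** With one landmark time for all patients, both groups are event-free at the start and share the same hazard afterwards, so the null ratio is 1.0. A landmark at each patient's own treatment end plus 24 weeks is not safe if duration depends on response and the hazard falls over time. Suppose SVR patients are treated for 48 weeks and others for 24, and the hazard is 0.10 per year until year 1 and 0.03 after.

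- SVR patients start at 1.385 years and have rate 0.03.
- Others start at 0.923 years, with 0.077 years at 0.10 and then two years at 0.03. Events are 0.0077 + 0.9923 × 0.0582 = 0.0655, person-time is 0.0766 + 1.926 = 2.003, and the rate is 0.0327.
- The null ratio is 0.03/0.0327 = 0.92. With 0.15 in the first year it is 0.87.

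**The case against.** **Time zero is not written into this comparison.** Section 8.7 names no clock for it, the consent wording in section 9.1 would suit one starting when treatment outcome is known, and listing SVR in a Cox model does not exclude a time-dependent term. This stands in part. A reader might infer that the protocol expressly fixes SVR as a baseline label from eltrombopag initiation. It does not. But section 8.1 places the three-year SVR comparison within follow-up from eltrombopag initiation, and Kaplan-Meier curves with a log-rank test between patients who did and did not attain SVR most naturally mean fixed groups. Taken together, the sections lead to the biased analysis unless something is added.

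**Decompensation does not preclude SVR.** This stands. The events in section 8.3.1 are ascites, encephalopathy and variceal bleeding, and nothing in the protocol says that they end therapy or make SVR impossible. A reader might infer immortal time for decompensation as strict as for death, or a rate ratio as low as 0.19 to 0.32. That range needs all 10% of events to occur on treatment, followed by 3% per year, and the documents support neither.

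**The comparison is minor.** The study is descriptive, section 8.5 says this comparison is not powered, and a separate sponsor study of 200 patients addresses the question. This limits the consequence. It does not answer the point, because low power widens the interval and leaves the bias in place, and section 8.9 does not list the bias as a limitation.

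**Conclusion.** The concern holds in direction. Followed as written, the SVR comparison is biased towards a protective effect: necessarily for death, and for decompensation as far as early events reduce the chance of SVR.

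The size cannot be taken from the documents. Under the assumptions shown, the null decompensation rate ratio is about 0.46 to 0.79 if on-treatment events preclude SVR, 0.68 to 0.89 if they halve it, and 1.0 if they have no effect. A reader might infer that the study is bound to report a benefit. The documents do not support that: with about 10 events expected (105 patients × 10%), chance could mask or exaggerate the bias, and a real SVR effect may also exist.

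The primary objective, incidence in a single cohort, is unaffected. This should be fixed, but it does not undermine the study.

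**What to change.** In section 8.7, state time zero for the SVR comparison and reconcile section 8.1 (three years from eltrombopag initiation) with section 9.1 (up to three years after treatment outcome is determined). Then specify one of the following:

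- **Time-dependent SVR.** Measure time from eltrombopag initiation. SVR switches on at the date it is determined, and events and person-time before that date count as not (yet) SVR.
- **One common landmark.** Choose a single time from eltrombopag initiation for all patients. Include only those alive, under follow-up and, for decompensation, event-free at that time. Group them by SVR status as known then, and count only later events and person-time.

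Apply the chosen rule to the rate ratio, Kaplan-Meier curves, log-rank test and Cox model alike. Report earlier events separately, and check proportional hazards instead of assuming it. A landmark tied to each patient's own end of treatment is best avoided, for the reason shown in the working.

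The cost is a wording change and lower precision. With 105 patients and 10% decompensation spread evenly over three years (10.5 events), about 7.2 fall after 0.923 years and 5.5 after 1.385 years. A reader might infer that follow-up must be extended to three years after treatment outcome. It need not be, and doing so would change the follow-up stated in section 8.1 against an end of data collection in 2018 (section 5).
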